5.6 Primary Objective #3: Evaluate Effectiveness of Risk Minimisation Activities

The receipt and use/read of effective risk minimisation activities will be summarised [addressed in Section 5.3]. To explore the effectiveness of the risk minimisation activities, assessment of physician behaviour in terms of compliance with key aspects of the SmPC including the use of the pre-infusion checklist and health provider education card will be described for the following parameters among enrolled patients in the registry:

- Appropriate patient selection for treatment with vernakalant IV (adherence to recommended indications and contraindications) [addressed in Sections 5.5 and 5.8]
- Administration and weight-based dosing of vernakalant IV, including patient monitoring during and after infusion [addressed in Section 5.5]
- Use of anti-arrhythmics before and after vernakalant IV [addressed in Section 5.9]
- Monitoring for the occurrence and incidence of serious adverse events (SAEs) and HOIs [addressed in Sections 5.4 and 5.7]

5.7 Secondary Objective #1: Counts and Rates of Serious Adverse Events (SAEs)

Per Secondary Objective #1, tables with counts and cumulative incidence of SAEs (including HOIs) will be provided and summarised by MedDRA system organ class (SOC), high level term (HLT), and preferred term (PT), and also stratified by outcome (recovered, recovered with sequelae, and not recovered) (**Tables 16.1a.1 to 16.1a.3**), fatal or non-fatal (**Tables 16.1b.1 to 16.1b.3**), and relationship to the study drug (definitely related, probably related, possibly related, probably not related, definitely not related) (**Tables 16.1c.1 to 16.1c.3**). Incidence is calculated as the number of patients who have a SAE starting during the study period, divided by the total number of patients in the analysis population set, times 100.

Characteristics of patients with SAEs, which may include medical history, presenting conditions, medication use, dosing/administration of vernakalant IV, and concomitant therapies, will be summarised in the narrative in a listing of individual SAEs in study reports (**Listing 2b**). Site-reported case narratives and clinical narrative from the medical monitor will be provided for each

SAE. Listings will be by event (i.e., patient with multiple events will be repeated for each event type) and will contain the patient's case narrative for each event.

5.8 Secondary Objective #2: Characterise Patients Administered Vernakalant IV by Medical History, Presenting Conditions and Other Baseline Characteristics

Pertaining to Secondary Objective #2 and Primary Objective #3, the number and percentage of patients greater than 18 years of age (adults) and patients administered vernakalant for recent onset atrial fibrillation (\leq 7 days duration for non-surgical atrial fibrillation and \leq 3 days duration for post-cardiac surgery atrial fibrillation) in accordance with the vernakalant Summary of Product Characteristics (SmPC) will be described (**Table 10**).

In addition, the number and percentage of patients with a reported contraindication for use as specified in the vernakalant IV SmPC will be described (**Table 11**). Specifically, the description will include the following conditions:

- Patients with systolic blood pressure <100 mm Hg
- Acute coronary syndrome (including myocardial infarction) within the last 30 days
- Patients with prolonged QT at baseline (uncorrected > 440 msec) in absence of pacemaker
- Severe aortic stenosis
- Severe bradycardia in the absence of a pacemaker
- Sinus node dysfunction in the absence of a pacemaker
- Heart block (second or third degree) in the absence of a pacemaker
- Patients with heart failure NYHA functional class III or NYHA functional class IV
- Use of class I or class III intravenous anti-arrhythmics within four hours prior to or after the start of vernakalant administration other presenting conditions and medical history at baseline will be summarised.

The following presenting conditions and medical history information will be reported in term of number and percentage (**Table 5**):

Presenting Conditions:

- Systolic blood pressure (mm Hg) as recorded most immediately prior to initial vernakalant infusion
- Diastolic blood pressure (mm Hg) as recorded most immediately prior to initial vernakalant infusion
- Heart rate (beats per minute) as recorded most immediately prior to initial vernakalant infusion)
- New York Heart Association (NYHA) functional class at hospital presentation (0, I, II, III, IV)

- History of heart failure (yes, no, unknown) and among these patients who had NYHA heart failure class III or IV at hospital presentation
- Previously documented left ventricular ejection fraction (LVEF, $\leq 30\%$, $> 30 - \leq 50\%$, $> 50\%$, Not Available). LVEF information will be reported as recorded in the electronic case report form (eCRF) from either (1) the baseline echocardiogram (performed during the index hospitalization, but prior to vernakalant administration), if available, or (2) the baseline medical history CRF, which records previously documented LVEF for patients with a reported history of heart failure. If data are available in both forms, the data with the most recent associated date will be included. Otherwise patients will be classified as LVEF $> 35\%$ or “not available”. The “not available” classification includes patients with no LVEF information on either the medical history or echocardiogram data collection forms. Additional details regarding LVEF (%), such as range of LVEF, may be reported, if available.
- Clinically meaningful valvular stenosis, as per physician assessment (yes, no, unknown), and among these patients who have a history of valve replacement and had heart valve surgery during index hospitalisation
- Cardiomyopathy (yes, no, unknown, and whether hypertrophic obstructive cardiomyopathy, restrictive cardiomyopathy or other)
- Constrictive pericarditis (yes, no, unknown)
- Advanced hepatic impairment (yes, no, unknown)
- Elevated liver enzymes (inclusive of possible abnormal liver function or liver injury), defined as an increase above ULN for alanine aminotransferase (ALT), aspartate aminotransferase (AST), total bilirubin (TB) or conjugated bilirubin based on recommended algorithms to define abnormal liver function and liver injury in the literature [1,2]. Patients must have at least one laboratory value available for ALT, AST, TB or conjugated bilirubin to be eligible to determine if liver enzymes are elevated for this calculation.
- Estimated GFR calculated by abbreviated MDRD. MDRD will be calculated for patients with available race information [1].

Medical History:

- Pacemaker implantation
- Implantable cardioverter-defibrillator (ICD)
- History valve replacement
- History of vascular surgery
- History of left atrial clot
- History of left ventricular hypertrophy
- History of hypertension
- History of angina

- History of stroke
- History of diabetes
- History of hyperlipidaemia
- Current smoking status
- History of hyperthyroidism
- History of rheumatic heart disease

In addition, a summary of atrial fibrillation disease history and current episode will be presented separately to further characterise the population (**Table 6**). The following information will be described:

- Duration of current AF (hours). Duration of current AF is defined as date/time of vernakalant IV administration minus date/time of current AF episode onset and will be expressed both as a continuous variable and as a categorical variable (<3, 3-24, 24-48, 48-168, >168 hours).
- Time since first AF diagnosis (days)
- Lone atrial fibrillation (yes, no, unknown)
- Type of AF (first diagnosed, paroxysmal, persistent, long-standing persistent, permanent, post-operative, unknown/ not assessed) [4]
- Symptoms of AF, including shortness of breath, palpitation/irregular heartbeat, chest pain/angina, dizziness/light-headedness, syncope/ near syncope, other (yes, no unknown/not assessed. Note: “unknown/not assessed” is not available for “other”).

Lastly, selected concomitant medications will be presented for patients receiving vernakalant as shown in the example **Table 7**. The frequency for selected concomitant medications will be reported for the following time periods: within 24 hours prior to hospitalization or medical encounter; during hospitalization or medical encounter but prior to vernakalant administration; during hospitalization or medical encounter but subsequent to vernakalant administration; and any time within 24 hours prior to or during hospitalization or medical encounter. For each time interval, the denominator will be the total number of patients enrolled and treated with vernakalant. Additional concomitant medications may be included in Table 7 for specific medications or classes that are reported in a minimum of 5% of patients after the minimum enrolment of 100 patients has been reached. Note: Concomitant medications will be coded using the WHO-DD, Format C (01Mar2011) and the ATC Classification System. However, for the purposes of this study, medications sotalol and sotalol hydrochloride will be re-classified for consistency with the Vaughan Williams Classification of Antiarrhythmic Drugs listed in the next section [5]. Thus study programmers will manually reclassify sotalol from the assigned ATC code of C07AA (Beta Blocking Agents, Non-Selective) to the ATC code C01BD (Antiarrhythmics, Class III) in the analysis datasets.

5.9 Secondary Objective #3: Concomitant Therapies to Restore Sinus Rhythm including Anti-Arrhythmic Medication, Electrical Cardioversion, Ablation, and Maze Procedures

Corresponding to Secondary Objective #3, tables will summarise the frequency of concomitant therapies (pharmacological cardioversion, electrical cardioversion, and surgical treatment) to restore sinus rhythm for atrial fibrillation during the medical encounter. Each patient may receive multiple pharmacological and electrical cardioversion treatments (episodes) and tables will summarise patient- and episode-level data.

Summary of the use of intravenous and oral pharmacological cardioversion before, concurrent with, and/or after vernakalant IV includes (**Table 12a, 12b**):

- Administration of other anti-arrhythmic agents for pharmacologic cardioversion (yes, no) (per patient)
- Number of anti-arrhythmic administrations (total episodes)
- Rhythm disorder type for pharmacological cardioversion (atrial fibrillation, atrial flutter, ventricular tachycardia, ventricular fibrillation, other) (per episode)
- Class of anti-arrhythmics (IA, IB, IC, II, III, IV) (per episode)
- Specific intravenous or oral anti-arrhythmic drugs (e.g., Flecainide, Propafenone, Amiodarone, Ibutilide), by class (per episode)

Note: Anti-arrhythmic class will be derived for each pharmacological cardioversion for each drug field based on ATC classification and the following clinical guidelines [6,8,9] Note: for the purposes of this study, sotalol and sotalol hydrochloride will be re-classified from beta blocking agents to antiarrhythmics, Class III for consistency with the Vaughan Williams Classification of Antiarrhythmic [5]. Study programmers will manually reclassify sotalol from the assigned ATC code of C07AA (Beta Blocking Agents, Non-Selective) to the ATC code C01BD (Antiarrhythmics, Class III) in the analysis datasets.

| Vaughn Williams Class | Examples of Anti-Arrhythmic Drugs |
|-----------------------|--|
| IA | Disopyramide Procainamide Quinidine |
| IB | Lidocaine Mexiletine |
| IC | Flecainide Propafenone |
| II | Beta blockers (e.g., propranolol) |
| III | Amiodarone Bretynium Dofetilide Dronedarone Ibutilide Sotalol |

| Vaughn Williams Class | Examples of Anti-Arrhythmic Drugs |
|-----------------------|--|
| IV | Nondihydropyridine calcium channel antagonists (verapamil and diltiazem) |
| Other AA/Class V | Adenosine |

Characteristics of conditions and classification of treatments will be summarized based on number of patients who received other IV or ORAL Anti-Arrhythmic agents respectively and number of episodes within corresponding timeframes (**Table 12a, 12b**).

Summary of the use of electrical cardioversion before, within 90 minutes from the start of the first vernakalant IV infusion, and at any time after the start of the first vernakalant IV infusion includes (**Table 13a**):

- Electrical cardioversion used to restore sinus rhythm (yes, no) (per patient)
- Total number of electrical cardioversion episodes (all patients)
- Successful restoration of sinus rhythm (yes, no) (per episode)
- Type of electrical cardioversion for all rhythm disorders (atrial fibrillation, atrial flutter, ventricular tachycardia, ventricular fibrillation) and type of defibrillator. Number of patients receiving electrical cardioversion for each rhythm disorder will be presented.

Surgical procedures (**Table 13b**), including such procedures as ablation and maze, will be stratified by whether they were administered prior to the first vernakalant infusion and subsequent to the start of the first vernakalant infusion.

Concomitant therapies (**Table 7**) will be stratified by the timing of administration relative to vernakalant IV administration (prior, concurrent, or subsequent), based on the start and stop date/time of the concomitant treatment and administration.

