### **The secondary objective of the study are to:**

1. Summarise the count and rate of all serious adverse experiences (SAEs) for HOIs that may not meet the definitions of medically significant HOIs as defined above, as well as all other SAEs reported during treatment and during the first 24 hours after the last infusion of vernakalant IV or until discharge/end of medical encounter, whichever occurs earlier.
2. Characterise patients administered vernakalant IV in terms of patient demographics, medical history, and presenting conditions. Specific conditions to be summarised include:
  - Heart failure, New York Heart Association (NYHA) class
  - Prolonged QT, severe bradycardia, sinus node dysfunction, second or third degree heart block, clinically meaningful valvular stenosis, hypertrophic obstructive cardiomyopathy, restrictive cardiomyopathy, constrictive pericarditis
  - History of hyperthyroidism
  - Severe aortic stenosis, Low systolic blood pressure (BP)
  - Recent acute coronary syndrome (including myocardial infarction [MI])
  - Presence of pacemaker/year of implantation
  - Hepatic impairment
3. Document the administration of concomitant treatment modalities to restore or maintain sinus rhythm during the hospitalisation/medical encounter (e.g., oral or IV anti-arrhythmics, electrical cardioversion, ablation, Maze procedure).
4. Describe the rate of successful cardioversion to sinus rhythm for at least one minute within 90 minutes of start of first vernakalant IV administration and time (in hours) from vernakalant infusion until discharge/end of medical encounter.

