The clinically significant adverse reactions discussed above are being monitored and have been identified as potential risks in the vernakalant IV Risk Management Plan (RMP). In addition, specific contraindications such as heart failure (NYHA III and IV), severe aortic stenosis, myocardial infarction (MI) or acute coronary syndrome (ACS) in 30 days prior to administration, prolonged QT at baseline (uncorrected  $>$  440 msec), severe bradycardia, sinus node dysfunction, second degree and third degree heart block in the absence of a pacemaker, and use of intravenous rhythm control antiarrhythmics (class I and class III) within 4 hours prior to vernakalant IV administration are also being monitored.

Key prescribing information from the SmPC are included as part of the package leaflet in the Brinavess™ packaging, and distributed with the product directly to the point-of care site. Additionally, the SmPC accompanies the HCP education card packs that are distributed to all anticipated prescribers and users of the product. In addition to this, SmPCs are handed out at the occasion of each customer contact, at national and international conferences, as well as in local educational events. The SmPC is accessible on Cardiome's Brinavess™ website through hyperlinks to the EMA website. The SmPC is

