**Exclusion Criteria**

The exclusion criteria for enrolment are:

1. Patients with the following contraindications:
  - Hypersensitivity to the active substance or to any of the excipients.
  - Patients with severe aortic stenosis, patients with systolic blood pressure  $< 100$  mm Hg, and patients with heart failure class NYHA III and NYHA IV.
  - Patients with prolonged QT at baseline (uncorrected  $> 440$  msec), or severe bradycardia, sinus node dysfunction or second degree and third degree heart block in the absence of a pacemaker.
  - Use of intravenous rhythm control antiarrhythmics (class I and class III) within 4 hours prior to, as well as in the first 4 hours after, BRINAVESS™ administration.
  - Acute coronary syndrome (including myocardial infarction) within the last 30 days.
2. Enrolment in an investigational drug or device clinical trial in the 30 days prior to study enrolment. Participation in another non-interventional drug or device study or registry is permitted.

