- Patients with at least one of the following contraindications: baseline systolic blood pressure < 100 mmHg, MI/ACS past 30 days, severe aortic stenosis, severe bradycardia in absence of pacemaker, prolonged QT at baseline (uncorrected > 440 msec) in absence of pacemaker, sinus node dysfunction in absence of pacemaker, 2nd or 3rd degree heart

block in absence of pacemaker, heart failure NYHA functional class III or IV, use of class I or class III intravenous anti-arrhythmics within 4 hours before, or within 4 hours after, the start of first vernakalant infusion).

In addition, the effectiveness of vernakalant will be evaluated by the indication of use for which vernakalant IV was prescribed (i.e., conversion of atrial fibrillation for non-surgery patient and conversion of atrial fibrillation for post-cardiac surgery patients).

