| n | xx | xx | xx |
| Yes | xx (xx.x%) | xx (xx.x%) | xx (xx.x%) |
| No | xx (xx.x%) | xx (xx.x%) | xx (xx.x%) |
| Missing/Unknown | xx (xx.x%) | xx (xx.x%) | xx (xx.x%) |
| Prolonged QT at baseline (uncorrected > 440 msec) in absence of pacemaker³ | | | |
| n | xx | xx | xx |
| Yes | xx (xx.x%) | xx (xx.x%) | xx (xx.x%) |
| No | xx (xx.x%) | xx (xx.x%) | xx (xx.x%) |
| Missing/Unknown | xx (xx.x%) | xx (xx.x%) | xx (xx.x%) |
| Sinus node dysfunction in absence of pacemaker³ | | | |
| n | xx | xx | xx |
| Yes | xx (xx.x%) | xx (xx.x%) | xx (xx.x%) |
| No | xx (xx.x%) | xx (xx.x%) | xx (xx.x%) |
| Missing/Unknown | xx (xx.x%) | xx (xx.x%) | xx (xx.x%) |
| Heart block (2nd of 3rd degree) in absence of pacemaker³ | | | |

| Characteristics | Prospective Patients (N=xxx) | Retrospective Patients (N=xxx) | Analysis Set (N=xxx) |
|--|---------------------------------|--------------------------------------|-------------------------|
| n | xx | xx | xx |
| Yes | xx (xx.x%) | xx (xx.x%) | xx (xx.x%) |
| No | xx (xx.x%) | xx (xx.x%) | xx (xx.x%) |
| Missing/Unknown | xx (xx.x%) | xx (xx.x%) | xx (xx.x%) |
| Heart failure NYHA functional class III or IV¹ | | | |
| n | xx | xx | xx |
| Yes | xx (xx.x%) | xx (xx.x%) | xx (xx.x%) |
| No | xx (xx.x%) | xx (xx.x%) | xx (xx.x%) |
| Missing/Unknown | xx (xx.x%) | xx (xx.x%) | xx (xx.x%) |
| Use of class I or class III intravenous anti-arrhythmics within four hours prior to the start of vernakalant administration or four hours subsequent to the start of vernakalant administration⁴ | | | |
| n | xx | xx | xx |
| Yes | xx (xx.x%) | xx (xx.x%) | xx (xx.x%) |
| No | xx (xx.x%) | xx (xx.x%) | xx (xx.x%) |
| Missing/Unknown | xx (xx.x%) | xx (xx.x%) | xx (xx.x%) |
| Patients with at least one contraindication | | | |
| n | xx | xx | xx |
| Yes | xx (xx.x%) | xx (xx.x%) | xx (xx.x%) |
| No | xx (xx.x%) | xx (xx.x%) | xx (xx.x%) |
| Missing/Unknown | xx (xx.x%) | xx (xx.x%) | xx (xx.x%) |

Note: Total n for each variable includes non-missing observations. Percentages, where applicable, are calculated with non-missing observations in denominator unless otherwise noted.

¹As recorded on the Baseline (Personal Data, Physical Measurements, Vital Signs and Cardiac Info) Case Report Form (CRF)

²As recorded on the Baseline (Conditions, Presenting Conditions) CRF.

³As recorded on the Baseline (Conditions, Presenting Conditions) or ECG CRF.

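### The only planned baseline QT row is restricted to patients without a pacemaker, so no table gives the overall prolonged-QT count, and the restriction needs reconciling with the protocol

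*SAP*

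**What the plan says.** Secondary Objective 2 (Protocol synopsis, sections 4 and 10.3; SAP 2.2) asks for a summary of conditions that begins "Prolonged QT, severe bradycardia, sinus node dysfunction, second or third degree heart block, clinically meaningful valvular stenosis". It attaches no pacemaker condition and gives no QT threshold.

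The contraindication wording differs by place:

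- **Protocol section 3** gives one comma-separated list with a single trailing qualifier: "440 msec), severe bradycardia, sinus node dysfunction, second degree and third degree heart block in the absence of a pacemaker".
- **Annex for German sites, Exclusion Criteria**, puts a comma and a conjunction between QT and the rest: "msec), or severe bradycardia, sinus node dysfunction or second degree and third degree heart block in the absence of a pacemaker".
- **SAP 5.8**, which defines Table 11, attaches the qualifier to QT itself: "Patients with prolonged QT at baseline (uncorrected > 440 msec) in absence of pacemaker".
- **SAP 4.3** uses the same condition to remove patients from the SmPC-conform effectiveness subgroup: "prolonged QT at baseline (uncorrected > 440 msec) in absence of pacemaker".
- **The Table 11 shell** repeats it as a row label: "Prolonged QT at baseline (uncorrected > 440 msec) in absence of pacemaker". The table closes with a summary row, "Patients with at least one contraindication".

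Baseline QT interval is a listed data element (Protocol 7.1.1), and a Table 11 footnote names the ECG form as one source for the QT row.

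**The concern.** Two issues meet in one table row.

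The first is a reporting gap. Secondary Objective 2 names prolonged QT as a condition to be summarised, and the SAP reports it only for patients without a pacemaker. This gap does not depend on how the label is read.

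The second is the contraindication itself. SAP 5.6 uses the Table 11 material to judge appropriate patient selection under Primary Objective 3, and SAP 4.3 uses the same criteria to define who was treated according to the SmPC. If QT above 440 msec contraindicates treatment whether or not a pacemaker is present, the any-contraindication count is too low and the SmPC-conform subgroup contains contraindicated patients. On that reading the annex would also keep such a patient out of the registry at a German site, while the SAP would count the same patient elsewhere as having no QT contraindication.

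**Working it through.** No sample-size or error-rate figure is involved. The check sets the texts side by side, searches the planned outputs and traces one patient.

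**Step 1: does the pacemaker qualifier attach to QT?**

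| Place | Attached to QT? |
|---|---|
| Secondary Objective 2, protocol and SAP | No qualifier present |
| Protocol section 3 | Can be read either way |
| German annex | Stand-alone QT is the more natural reading; the other is grammatically possible |
| SAP 4.3, SAP 5.8, Table 11 | Yes, explicitly |

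**Step 2: is an unrestricted QT count planned anywhere?**

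- Table 5 (text in SAP 5.8 and shell): no QT row. Pacemaker status is tabulated alone.
- Table 11: one QT row, the restricted one.
- Table 18 (missing critical fields): QT is not listed.
- SAP Appendix 2: contains a QT-prolongation term, but as a serious adverse event code, not a baseline condition.

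**Step 3: trace a patient with QT above 440 msec and a pacemaker.**

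- Table 11 QT row: No.
- Any-contraindication row: No, provided no other contraindication is present.
- Table 15b subgroup: retained, provided also that the age, indication and AF-duration criteria are met.

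**Step 4: what can be recovered from the planned tables?** Among patients with QT above 440 msec, let a = no pacemaker, b = pacemaker, c = pacemaker status unknown. Let P be the number with a pacemaker in Table 5, assuming Tables 5 and 11 use the same pacemaker variable.

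- Table 11 reports a.
- The objective's count is a + b + c.
- Because 0 ≤ b ≤ P, the tables bound a + b between a and a + P. They do not identify it, since QT is never crossed with pacemaker status.
- The SAP does not say whether c falls under No or under Missing/Unknown.

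On the stand-alone reading, the any-contraindication total rises by the part of b with no other contraindication, so by at most b. The Table 15b subgroup shrinks by at most that same number.

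**Step 5: size.** The number affected is b, the number treated × the proportion with a pacemaker × the proportion of those with QT above 440 msec. The documents give neither proportion, so b cannot be calculated.

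**Step 6: reach.** SAP 5.4 divides HOI counts by all patients enrolled and treated. Contraindication status does not enter that calculation.

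**The case against.** The strongest reply is that the SAP has simply resolved an ambiguity, and has done so consistently in three places. The annex item is one sentence with one trailing pacemaker phrase, which can govern all four conditions. Section 3 is looser still. The annex sets eligibility at German sites and is not the label, and the SmPC that the SAP says it follows is not among the documents. This stands. A reader might infer that the SAP has added a condition the label lacks, or that the contraindication count is wrong. The documents do not support either inference; they show only that the wordings differ.

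A second reply is that Secondary Objective 2 names topics and does not define them. It also lists severe bradycardia, sinus node dysfunction and heart block without a qualifier, and Table 11 restricts those rows in the same way. This is fair, and it means a missing qualifier in the objective does not by itself dictate how a contraindication is defined. QT still differs in one respect: for the other three the annex plainly carries the qualifier, while for QT it more naturally does not. Nor does the reply remove the gap, because a named condition has no overall count.

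Third, the row label states its restriction, so a No does not assert a normal QT. That is correct. What a reader of the table lacks is the count of patients with both features.

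Finally, QT is collected and SAP section 5 allows ad hoc analyses at the sponsor's request. Nothing is lost from the database, but an optional request does not replace planned output for a stated objective.

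**Conclusion.** The point holds as a minor reporting gap plus a wording conflict to be reconciled. Followed as written, the plan does not report how many treated patients had prolonged QT, on any reading of the label. Whether the any-contraindication total is understated, and whether the Table 15b subgroup includes contraindicated patients, depends on which reading is right. This review does not decide that.

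The consequence is limited to descriptive contraindication counts and one secondary effectiveness subgroup. A reader might infer that the primary safety result is affected; it is not. A reader might also try to size the problem from assumed pacemaker and QT frequencies. Any such figure would reflect only the assumptions, since the documents supply neither frequency. The number could be very small.

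**What to change.** 1. In Table 11, report QT above 440 msec for all treated patients, with separate sub-rows for pacemaker present, absent and unknown. Keep unknown apart from absent, since Table 5 already distinguishes them.
2. Reconcile Protocol section 3, the German annex, SAP 4.3, SAP 5.8 and Table 11 against the SmPC, and state one definition.
3. Until that is done, show the any-contraindication total and the Table 15b subgroup under both readings.
4. Optionally, add baseline QT as a continuous variable to Table 5.

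The cost is a short SAP wording change and a few table rows from data already collected. The contraindication count may come out slightly higher and the Table 15b subgroup slightly smaller under one of the readings.
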